4.3.1.2 Other Protocol-Mandated Asthma Medications

All patients must be on a stable asthma treatment regimen consisting of ICS therapy plus at least one additional controller medication (see Section 4.4.1 for details). Refer to the prescribing information for the formulation, packaging, and handling of these medications.

4.3.2 Dosage, Administration, and Compliance

4.3.2.1 MSTT1041A and Placebo

Patients who meet eligibility criteria during the screening period will be enrolled and receive a single-blind dose of placebo at the run-in visit (Week 0). At Week 2, patients deemed eligible will be randomly allocated to receive treatment with MSTT1041A 70 mg, 210 mg, or 490 mg or placebo, administered as four SC abdominal injections every 28 (± 5) days (Q4W) from the randomization visit (Week 2) through Week 50. With the exception of the single-blind placebo dose, no more than one dose should be administered within any 21-day period. If the dosing window is missed, that dose will not be administered, and the next dose will be administered at the next scheduled dosing date. There will be no dose adjustments in this study.

Study drug administration must occur after all other procedures have been completed at each clinic visit. Study drug will be administered at the study site by trained medical personnel. Each dose of study drug (MSTT1041A or placebo) will be administered as four SC injections (one 1-mL injection and three 2-mL injections, for a total of 7 mL), one in each quadrant of the abdomen. All patients will be held for observation for at least 2 hours after each of the first six doses (i.e., Week 0 through Week 18, including the single-blind placebo dose). Dosing on subsequent dosing days should include a minimum length of observation time of 15 minutes, and longer in the event of an injection site reaction, approximately 60 minutes or other, as determined by the investigator.

Patients who are unable to tolerate study drug will discontinue treatment but will be asked to continue with study assessments. Study drug may be resumed after the events resolve, if the investigator determines that the event was not related to study drug and the investigator and Medical Monitor agree that it is appropriate for the patient to resume study drug. Section 5.1.2.2 provides specific guidelines for withholding or discontinuing study drug for patients who experience hepatotoxicity.

Any overdose or incorrect administration of study drug should be noted on the Study Drug Administration electronic Case Report Form (eCRF). Adverse events associated with an overdose or incorrect administration of study drug should be recorded on the Adverse Event eCRF.

4.3.2.2 Other Protocol-Mandated Asthma Medications

All patients must be on a stable asthma treatment regimen consisting of ICS therapy plus at least one additional controller medication. Refer to Section 4.4.1 for details regarding asthma treatment regimens.

4.3.3 Investigational Medicinal Product Accountability

All IMPs required for completion of this study (MSTT1041A and placebo) will be provided by the Sponsor where required by local health authority regulations. The study site will acknowledge receipt of IMPs, using the IxRS to confirm the shipment condition and content. Any damaged shipments will be replaced.

IMPs either will be disposed of at the study site according to the study site's institutional standard operating procedure or will be returned to the Sponsor with the appropriate documentation. The site's method of IMP destruction must be agreed to by the Sponsor. The site must obtain written authorization from the Sponsor before any IMP is destroyed, and IMP destruction must be documented on the appropriate form.

Accurate records of all IMPs received at, dispensed from, returned to, and disposed of by the study site should be recorded on the Drug Inventory Log.

4.3.4 Post-Trial Access to MSTT1041A

Currently, the Sponsor (Genentech, a member of the Roche Group) does not have any plans to provide MSTT1041A or any other study treatments or interventions to patients who have completed the study. The Sponsor may evaluate whether to continue providing MSTT1041A in accordance with the Roche Global Policy on Continued Access to Investigational Medicinal Product, available at the following Web site:

http://www.roche.com/policy_continued_access_to_investigational_medicines.pdf

4.4 ASTHMA THERAPY AND CONCOMITANT THERAPY

Asthma medications used by the patient from 12 months prior to initiation of study drug (Week 0) through the end-of-study visit should be recorded on the appropriate eCRF. Other medications (e.g., prescription drugs, over-the-counter drugs, vaccines, herbal or homeopathic remedies, nutritional supplements) used by the patient within 3 months prior to screening through the end-of-study visit should be recorded on the Concomitant Medications eCRF.

Patients should not be asked to alter their standard therapy in any way until the informed consent process is complete.

4.4.1 Required Asthma Controller Therapy

All patients will continue on a stable asthma treatment regimen that is consistent with GINA guidelines, as outlined below:

- ICS therapy at a total daily dose of ≥ 500 μg of fluticasone propionate or equivalent plus at least one additional controller medication, for ≥ 3 months prior to screening, with no changes within 4 weeks prior to screening or during the screening or run-in periods and no anticipated changes in dosing regimens throughout the study
 - For patients receiving total daily dose of $> 500\mu\text{g}$ of fluticasone propionate or equivalent, they may receive one or more of the following additional controller medications: LABA, LTM, LAMA, or long-acting theophylline preparation.
 - For patients receiving total daily dose equal to 500 μg of fluticasone propionate or equivalent, at least one of their additional controller medication must be LABA.

Any changes to the formulation or dose of ICS or any additional controller medications should be avoided, with the exception of the theophylline dose, which may be adjusted as appropriate on the basis of serum theophylline levels. If changes to the ICS brand or formulation are unavoidable, the patient may be switched to another ICS brand or formulation at a dose equivalent to the ICS dose that the patient was receiving at study entry (please see [Appendix 3](#) for examples of ICS dose equivalence information). All changes to a patient's controller medications should be documented on the eCRF.

In order to maintain stable controller medication doses, patients may not use an ICS/LABA combination inhaler (i.e., single maintenance and reliever therapy) as rescue therapy.

Restrictions on the timing of administration of bronchodilators are described in Section [4.4.5](#).

4.4.2 Short-Acting Rescue Therapy

It is expected that the majority of patients will be using short-acting β -agonist (SABA) or short-acting muscarinic antagonist (SAMA) therapy for symptoms of uncontrolled asthma per existing treatment guidelines. Combination SABA or SAMA inhalers (e.g., albuterol/ipratropium) are also permitted. Short-acting rescue therapy must be administered via the patient's prescribed inhaler or nebulizer.

Any short-acting therapy that is prescribed as asthma rescue medication over the course of the study or administered during hospitalization or an emergency department, urgent care visit, or urgent unscheduled office visit should be documented on the appropriate eCRF.

Restrictions on the timing of administration of SABA or SAMA therapy relative to PEFR and spirometry measurements are described in Section [4.4.5](#).

4.4.3 Systemic Corticosteroid Use

Patients who require any systemic corticosteroids (oral, IV, or IM) within 4 weeks prior to screening or during the screening or run-in periods will not be eligible for the trial (see Section 4.1.2).

The use of systemic corticosteroids is permitted for acute patient management after randomization. Corticosteroids used for treatment of asthma (e.g., an acute exacerbation event as defined in Appendix 12) should be documented on the appropriate eCRF. Whereas systemic corticosteroids should not be used other than for asthma exacerbation, in the event that they are used to treat other medical conditions, this should be documented on the Concomitant Medications eCRF.

4.4.4 Asthma Therapy and Concomitant Therapy Restrictions

Asthma therapy and concomitant therapy restrictions are summarized in Table 2.

Table 2 Asthma Therapy and Concomitant Therapy Restrictions

Medication	Restrictions ^a
ICS therapy	On a stable regimen for ≥ 3 months prior to screening, with no changes within 4 weeks prior to screening, during the screening or run-in periods, or during the treatment period
LABA therapy LTMs LAMA therapy	No changes in dose or initiation of therapy within 4 weeks prior to screening, during the screening or run-in periods, or during the treatment period
Long-acting theophylline preparations	No changes in dose or initiation of therapy within 4 weeks prior to screening, during the screening or run-in periods, or during the treatment period, except for dose adjustments as appropriate on the basis of serum theophylline levels
Allergen immunotherapy	No changes in dose or initiation of therapy within 3 months prior to screening, during the screening or run-in periods, or during the treatment period Must not be administered on the same day as study drug
Maintenance oral corticosteroids (daily or every other day)	Prohibited within 3 months prior to screening
Systemic corticosteroids (oral, IV, or IM)	Prohibited within 4 weeks prior to screening and during the screening and run-in periods Prohibited for treatment of any condition other than asthma exacerbations during the 52-week double-blind treatment period
Intra-articular corticosteroids Phosphodiesterase-4 inhibitors (e.g., roflumilast) Live or live, attenuated vaccines Immunoglobulin or blood products	Prohibited within 4 weeks prior to screening, during the screening and run-in periods, and during the 52-week double-blind treatment period

Table 2 Asthma Therapy and Concomitant Therapy Restrictions (cont.)

Medication	Restrictions ^a
Maintenance oral and SC β -agonist therapy (e.g., terbutaline)	Prohibited within 2 weeks prior to screening, during the screening and run-in periods, and during the 52-week, double-blind, treatment period
Investigational therapy, including investigational use of a formulation of an approved drug ^b	Prohibited within 3 months or 5 drug half-lives prior to screening (whichever is longer), during the screening and run-in periods, and during the 52-week, double-blind treatment period
Licensed biologic agents (e.g., omalizumab, mepolizumab, suplatast)	Prohibited within 3 months or 5 drug half-lives prior to screening (whichever is longer), during the screening and run-in periods, and during the 52-week, double-blind treatment period
Immunomodulatory, immunosuppressive, or experimental anti-inflammatory therapy other than biologic agents or corticosteroids (see separate exclusions above)	Prohibited within 3 months or 5 drug half-lives prior to screening (whichever is longer), during the screening and run-in periods, and during the 52-week, double-blind treatment period
Maintenance oral or inhaled antibiotics β -blocking agents (topical, oral, or other systemic) Homeopathic medications, herbal medications, acupuncture, or hypnosis therapy Maintenance intermittent positive pressure ventilation physiotherapy Maintenance bilevel positive airway pressure therapy	Prohibited within 2 weeks prior to screening, during the screening and run-in periods, and during the 52-week double-blind treatment period
Bronchial thermoplasty	Prohibited within 24 months prior to screening, during the screening and run-in periods, and during the 52-week, double-blind, treatment period
Pulmonary rehabilitation	Prohibited except on an outpatient basis for patients who have been participating for ≥ 6 months prior to screening and will continue to participate during the 52-week, double-blind, treatment period

ICS = inhaled corticosteroid; IM = intramuscular; IV = intravenous; LABA = long-acting β -agonist; LAMA = long-acting muscarinic antagonist; LTM = leukotriene modifier; SC = subcutaneous.

^a The Medical Monitor should be consulted in cases of uncertainty.

^b Patients participating in a clinical trial that has not been unblinded should be assumed to have received the active drug.

Patients who take any prohibited concomitant medications should not necessarily be withdrawn from the study or discontinue study treatment, as described in Section 4.6. The Medical Monitor should be consulted to ensure that there are no safety risks associated with continuing study drug or if a study treatment interruption should be considered.

4.4.5 Medication Use prior to Peak Expiratory Flow Rate and Spirometry Measurements

Patients will measure PEFR once daily, prior to taking their morning controller medications (see Section 4.5.5.1 for details). At specified timepoints during the study, patients will undergo pre-bronchodilator spirometry measurements in the clinic (see Section 4.5.12.1 for details). Bronchodilator use is prohibited within a specified window prior to PEFR and pre-bronchodilator spirometry measurements, as follows:

- Twice-daily LABA and LAMA: prohibited within 12 hours prior to PEFR or spirometry
- Once-daily LABA and LAMA: prohibited within 24 hours prior to PEFR or spirometry
- SABA or SAMA: prohibited within 4 hours prior to spirometry

At screening, patients will undergo post-bronchodilator FEV₁ measurements. Up to 8 puffs of SABA or nebulized equivalent (e.g., 2 treatments with 2.5 mg albuterol/salbutamol) will be administered in a step-wise fashion, as described in Section 4.5.12.2.

4.5 STUDY ASSESSMENTS

Please see [Appendix 1](#) for the schedule of activities to be performed during the study.

At applicable sites, certain PK blood samples may be collected by a mobile nursing (MN) professional at the patient's home or another suitable location, to improve access and convenience for patients participating in the study. The Sponsor will select a healthcare company that will be responsible for providing MN services for participating sites (the MN vendor). The MN vendor is responsible for ensuring that all MN professionals are licensed, qualified, and in good standing, as per applicable regulations, and that appropriate background checks have been performed. If the investigator at a participating site determines that MN services are appropriate for a patient and the patient gives written informed consent to participate in MN visits, the MN network will communicate with the patient and the patient's site. MN visits will be scheduled on specified visit days, to allow for relevant assessments to be performed by the MN professional. A schedule for PK blood sample collection is provided in [Appendix 2](#).

4.5.1 Informed Consent Forms

Written informed consent for participation in the study must be obtained before performing any study-related procedures. Informed Consent Forms for enrolled patients and for patients who are not subsequently enrolled will be maintained at the study site.

4.5.2 Screening and Run-In Assessments

Patients who meet eligibility requirements during the 2- to 4-week screening period will be enrolled in the run-in period and will receive one single-blind dose of placebo at the run-in visit (Week 0).

Compliance with the required use of the eDiary and PEFr measurements as well as adherence with usual asthma controller medication regimen (see Section 4.1.1) must be demonstrated on 5 of 7 days during each of 2 consecutive weeks during the screening period. The earliest timepoint a patient can satisfy these eligibility criteria is 12 days after study consent. The 2- to 4-week screening period is intended to allow sufficient time for a patient to meet all eligibility requirements. However, if all eligibility requirements are met earlier (i.e., between 12 and 28 days after study consent), including confirmation of spirometry and ECG results, patients may be enrolled into the run-in period prior to the end of the 4 weeks of screening.

Patients who meet all eligibility requirements for enrollment in the run-in period with the exception of morning pre-bronchodilator FEV₁ of 40%-80% or post-bronchodilator reversibility of FEV₁ of $\geq 12\%$ and ≥ 150 mL are allowed up to two additional attempts to meet these two eligibility criteria within the screening period, if their morning pre-bronchodilator FEV₁ was between 35%-85%.

Patients who have received the single-blind placebo dose and not meet any of the following inclusion criteria or meet any of the following exclusion criteria at the randomization visit (Week 2) will be considered run-in failures and are not eligible for randomization (see Section 4.1.1.2 and Section 4.1.2.2):

- Inclusion Criteria:
 - No changes in ICS therapy or allowed controller medications (see Section 4.1.1.1) during the run-in period
 - Morning pre-bronchodilator FEV₁ of 40%–80% of predicted at randomization (Week 2) visit
- Exclusion Criteria:
 - Absolute percentage point change (increase or decrease) of 15 or more in morning pre-bronchodilator percentage of predicted FEV₁ from screening to the randomization visit
 - Absolute change (increase or decrease) in FeNO of ≥ 20 ppb and $\geq 40\%$ relative change between screening and randomization visits

These patients should be discontinued from the study and they are not eligible for re-screening. In addition, these patients should be informed that the first dose given at Visit 2 was a placebo and therefore there is no additional requirement for follow-up visits. However, patients who meet all eligibility requirements for enrollment in the double-blind treatment period with the exception of the morning pre-bronchodilator FEV₁ of 40%-80 are allowed one additional attempt to meet the criteria within the run-in period, if their morning pre-bronchodilator FEV₁ was between 35%-85%.

Note that after a patient has entered the run-in period and received the single-blind placebo dose, the patient cannot be re-screened for any reason.

Patients who are unable to complete or meet eligibility requirements during one screening period will be permitted to be re-screened twice for a total of up to three screenings.

Patients who fail to meet eligibility requirements ≤ 6 weeks after Informed Consent Form completion are required to repeat only the assessments that triggered screen failure.

Patients who fail to meet eligibility requirements > 6 weeks after Informed Consent Form completion are required to repeat the consent process and all screening and run-in assessments except TB screening, and hepatitis serologies. However, TB screening and hepatitis serologies should be repeated if the re-screening takes place > 6 months after initial screening.

If the second screening takes place within 6 weeks of the first screening, the patient must wait at least 4 weeks after the second screening for the third screening.

The investigator will maintain a screening log to record details of all patients screened and to confirm eligibility (if applicable).

4.5.3 Medical History and Demographic Data

Medical history includes, but is not limited to, clinically significant diseases, surgeries, reproductive status, smoking history, and use of alcohol and drugs of abuse. Targeted medical history will include specific information pertaining to diseases commonly associated with asthma, including, but not limited to, allergic rhinitis, atopic dermatitis, Type 2 diabetes, arthritis, osteoporosis, and heart disease. In addition, all medications (e.g., prescription drugs, over-the-counter drugs, vaccines, herbal or homeopathic remedies, nutritional supplements) used by the patient within 3 months prior to screening will be recorded. Asthma or allergy medications used within 12 months prior to screening will be recorded.

Demographic data will include age, sex, and self-reported race/ethnicity. Race/ethnicity is recorded because of the potential contribution of this variable to differences in observed pharmacokinetics, pharmacodynamics, toxicity, and/or response to treatment.

4.5.4 Atopy Status

The patient's atopy status (atopic or non-atopic) will be assessed during screening on the basis of historical documentation (e.g., patient's medical records). A patient is considered atopic if he or she has a positive result to any allergen demonstrated via historical allergy test (e.g., skin prick [wheal diameter ≥ 3 mm and documented negative control]), ImmunoCAP, or other specific IgE test. Regardless of atopy status, total and specific IgE testing will be performed at the randomization visit.

4.5.5 Assessments Completed by the Patient at Home

At the screening visit, patients will receive a peak flow meter that will be used for measuring PEFR and an eDiary that will be used for documenting asthma controller medication use and answering questions related to asthma symptoms, nighttime awakenings due to asthma, and use of short-acting rescue therapy. Patients will be given instructions on how to measure PEFR and record information in the eDiary at home on a daily basis. Site staff will review daily diary compliance at each subsequent visit and provide refresher training if needed.

4.5.5.1 Peak Expiratory Flow Rate

Patients will always measure PEFR in the morning (5:00–9:00 a.m.), at approximately the same time each day, prior to taking asthma controller medications. PEFR measurements should consist of three good efforts. Patients should complete their PEFR measure prior to taking their daily LABA and LAMA asthma controller medication as prescribed. PEFR windows are as follows:

- 12 hours after taking last dose of twice-daily LABA or twice-daily LAMA
- 24 hours after taking last dose of once-daily LABA or once-daily LAMA

On the days of study visits, if the patient had not performed the morning PEFR measurement before arrival at the clinic, the PEFR should be measured at the clinic.

4.5.5.2 Compliance with Asthma Controller Medication

Patients will be instructed to indicate whether or not they have taken their asthma controller medication each evening in the eDiary, during the screening period through Week 54, to monitor compliance with asthma controller medications. A copy of the Compliance with Asthma Controller Medication question is provided in [Appendix 11](#).

4.5.5.3 Daily Diary Symptom-Related Asthma Assessments

Patients will complete daily diary questions on the eDiary twice a day. The daily diary comprises morning items (to be completed when patients wake up) and evening items (to be completed at bedtime). The eDiary will remind patients when it is time to complete their diary. Details about the specific content are described in Morning Diary Questions and Evening Diary Questions below.

Morning Diary Questions

The morning diary (see [Appendix 4](#)) is comprised of 4 measures:

1. Asthma Daily Symptom Diary: Nighttime Symptoms

The Asthma Daily Symptom Diary (ADSD) (nighttime symptoms) includes 7 items that allow patients to rate the severity of their nighttime asthma symptoms since they went to bed the previous night on an 11-point scale ranging from 0 (none) to 10 (as bad as you can imagine).

A single item is used to assess each of the following concepts:

- Breathing
- Wheezing
- Shortness of breath
- Chest tightness
- Chest pain
- Cough
- Feeling of mucus in the chest

The ADSD nighttime symptom questions will be administered on 3 non-consecutive days during screening, run-in visit, randomization visit, daily for 7 days prior to Week 26, and daily for 7 days prior to Week 54.

2. Nighttime awakening due to asthma

Patients will respond to a single item asking whether they woke up because of their asthma symptoms (yes/no). The nighttime awakening due to asthma question will be administered every morning beginning at screening through Week 54.

3. Short acting symptom relief medication (short-acting rescue therapy)

Patients will be asked whether they used short-acting rescue medication to relieve their asthma symptoms during the night (yes/no). If “yes,” they will be asked whether they used an inhaler and whether they used a nebulizer (“breathing machine”) with instruction to choose “all that apply.” The short-acting symptom relief medication question will be administered every morning beginning at screening through Week 54.

4. Patient Global Impression of Severity

The Patient Global Impression of Severity (PGIS) completed in the morning diary asks patients to rate their nighttime asthma symptoms on an 11-point scale ranging from 0 (no symptoms) to 10 (as bad as you can imagine). The morning diary PGIS will be administered 4 times: at the run-in visit, the randomization visit, one day prior to Week 26 visit, and one day prior to Week 54 visit.

Evening Diary Questions

The evening diary ([Appendix 4](#)) is comprised of 3 measures.

1. Asthma Daily Symptom Diary: Daytime Symptoms

The ADSD (daytime symptoms) includes 7 items that allow patients to rate the severity of their daytime asthma symptoms since they got up in the morning on an 11-point scale ranging from 0 (none) to 10 (as bad as you can imagine).

A single item is used to assess each of the following concepts:

- Breathing
 - Wheezing
 - Shortness of breath
 - Chest tightness
 - Chest pain
 - Cough
 - Feeling of mucus in the chest
 - The ADSD daytime symptom questions will be asked daily from screening (Visit 1) through Week 54.
2. Short-acting symptom relief medication (short-acting rescue therapy)

Patients will be asked whether they used short acting rescue medication to relieve their asthma symptoms during the day (yes/no). If “yes,” they will be asked whether they used an inhaler and whether they used a nebulizer (“breathing machine”) with instruction to choose “all that apply.” The short-acting symptom relief medication question will be administered every evening beginning at screening through Week 54.

3. Patient Global Impression of Severity

The PGIS completed in the evening diary asks patients to rate their daytime asthma symptoms on an 11-point scale ranging from 0 (no symptoms) to 10 (as bad as you can imagine). The evening diary PGIS will be administered 5 times: at the run-in visit, the randomization visit, one day prior to Week 14 visit, one day prior to Week 26 visit, and one day prior to the Week 54 visit.

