6.9 EXPLORATORY PSYCHOMETRIC VALIDATION

Data from the ADSD nighttime symptoms, the PGIS nighttime symptoms, PGIS daytime symptoms, and PGIC symptoms questions will be used in separate analyses to explore psychometric properties of the ADSD. The exploratory psychometric validation endpoints are as follows:

- *Change in patient-reported nighttime asthma symptom severity, as measured by the ADSD, from baseline to Week 26 and Week 54*
- Patient's global impression of change from the randomization visit in asthma symptoms as assessed through use of the PGIC *from baseline to Week 26 and Week 54*
- Patient's global impression of severity of asthma symptoms as assessed through use of the PGIS at *Week 14, Week 26, and Week 54*

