Appendix 4 Daily Diary

MORNING DIARY QUESTIONS

Asthma Daily Symptom Diary (ADSD): Night Time Symptoms

[Administered on 3 non-consecutive days during screening; Run-in Visit; Randomization Visit; Daily for 7 days prior to Week 26; Daily for 7 days prior to Week 54]

[INSTRUCTION 1M] We would like you to complete this diary every morning when you get up.

[INSTRUCTION 2M] For each question, please choose the number that best describes your experience.

[INSTRUCTION 3M] Please answer each question by thinking about your asthma symptoms last night from when you went to bed until now.

[ITEM 1] Please rate your difficulty breathing at its worst since you went to bed last night.

0	1	2	3	4	5	6	7	8	9	10
None										As bad as you can imagine

[ITEM 2] Please rate your wheezing at its worst since you went to bed last night.

0	1	2	3	4	5	6	7	8	9	10
None										As bad as you can imagine

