4.2 DEFINITION OF BASELINE

Baseline is defined as the last available pre-treatment value taken on or before the day of randomization (Week 2 visit) for all assessments, with the exception of the following efficacy endpoints: patient-reported use of short-acting rescue therapy, and patient-reported daytime asthma symptom severity as measured by Asthma Daily Symptom Diary (ADSD). For these outcome measures, details for derivation of baseline values can be found in [Section 4.5.2](#).

Baseline measurements will be used for the summary of demographic characteristics, as well as for all change-from-baseline analyses of efficacy, safety, and PD endpoints (including change from baseline in FEV1, CGIC, blood eosinophil count, and FeNO, and improvement from baseline in AQLQ(S), ACQ-5, SGRQ, ACQ-7).

For endpoints that are defined in terms of change from baseline or improvement from baseline, patients who do not have a baseline measurement will be excluded from the analyses.

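### Read literally, SAP 4.2 gives the nighttime ADSD a one-morning baseline although five pre-treatment mornings are collected; averaging them would make the change score less noisy at no data cost

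*Protocol*

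**What the plan says.** **Collection.** Protocol 4.5.5.3 states: "The ADSD nighttime symptom questions will be administered on 3 non-consecutive days during screening, run-in visit, randomization visit". From the randomization visit on, the schedule reads "randomization visit, daily for 7 days prior to Week 26, and daily for 7 days prior to Week 54". Appendix 4 of the Protocol repeats this schedule. There are thus five mornings before treatment and seven before each follow-up visit.

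**Endpoint.** Protocol 6.9 lists "Change in patient-reported nighttime asthma symptom severity, as measured by the ADSD, from baseline to Week 26 and Week 54". The nighttime ADSD, PGIS and PGIC data "will be used in separate analyses to explore psychometric properties of the ADSD".

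**Baseline.** The opening of Protocol Section 6 leaves PRO scoring, missing-data handling and the definition of baseline to the SAP. SAP 4.2 answers: "Baseline is defined as the last available pre-treatment value taken on or before the day of randomization (Week 2 visit) for all assessments". It excepts two endpoints only, rescue-therapy use and the daytime ADSD.

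**Daytime comparison.** SAP 4.5.2 gives the daytime ADSD a baseline from two compliant screening weeks, a weekly average at follow-up, a minimum number of answered items per day and a missing-day rule. The SAP contains no corresponding text for the nighttime score.

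**The concern.** The two halves of one instrument are treated differently, and no reason is given. The daytime baseline averages up to 14 days. Under the general rule the nighttime baseline is one diary entry, normally from the randomization-visit morning. If that entry is missing, it is whichever earlier entry is latest, which is about two weeks older if it comes from the run-in visit.

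A change score carries the day-to-day noise of both of its ends. When one end is a single morning and the other averages seven, most of that noise comes from the single morning. Protocol 6.9 uses this change to study how the ADSD behaves as a measuring instrument. Avoidable noise lowers its reliability and can weaken its correlation with an external anchor.

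**Working it through.** The documents give no SD, reliability or correlation for the nighttime ADSD, so there is no stated figure to reproduce. Everything below is in units of the daily (within-patient, day-to-day) variance.

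**Inputs.** From Protocol 4.5.5.3: 1 baseline morning used (SAP 4.2 read literally), 5 collected, 7 at each follow-up. Inferred from the daytime rule in SAP 4.5.2: follow-up is the mean of the seven mornings. Assumed: AR(1) correlation φ of 0 to 0.6 between consecutive days.

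**Step 1: noise in the change score.** The variance of a 7-day mean is v7 = [7 + 2·Σ(7−k)φ^k]/49, with k from 1 to 6. Noise is 1 + v7 with one baseline morning and 0.2 + v7 with the mean of five mornings treated as independent. The baseline morning's share of the noise is 1/(1 + v7).

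| φ | v7 | one morning | baseline share | five mornings | reduction |
|---|---|---|---|---|---|
| 0 | 0.143 | 1.143 | 87.5% | 0.343 | 70% |
| 0.2 | 0.202 | 1.202 | 83.2% | 0.402 | 67% |
| 0.4 | 0.288 | 1.288 | 77.6% | 0.488 | 62% |
| 0.6 | 0.423 | 1.423 | 70.3% | 0.623 | 56% |

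At φ = 0 the noise SD falls by 45%, since √(0.343/1.143) = 0.55. The five mornings are not strictly independent. As an unfavourable example, take φ = 0.6 with the three screening mornings and the run-in visit each two days apart. The mean of five then has variance [5 + 2(3·0.36 + 2·0.13 + 0.05)]/25 ≈ 0.31. The total is 0.73 against 1.42, still a reduction of about 48%.

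**Step 2: share of the whole change score.** Let ρ be the single-day ICC and r the correlation of true levels between baseline and follow-up, both assumed. With independent days and total variance scaled to 1, true change has variance 2ρ(1−r). The baseline share of total variance is (1−ρ)/[(1−ρ)·8/7 + 2ρ(1−r)]. For ρ from 0.4 to 0.9 and r from 0.3 to 0.9 this runs from 7% to 78%.

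**Step 3: reliability and the PGIC.** Reliability is true-change variance divided by true-change variance plus noise. If true-change variance equals daily variance (assumption), it is 1/2.143 = 0.47 with one morning and 1/1.343 = 0.74 with five. If the PGIC is unrelated to the noise of the baseline mornings, the one-morning correlation is √(2.143⁻¹/1.343⁻¹) = 0.79 of the five-morning one. At the extremes of Step 2 the factor is √(0.104/0.280) = 0.61 (ρ = 0.4, r = 0.9) and √(0.917/0.974) = 0.97 (ρ = 0.9, r = 0.3).

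**Step 4: the PGIS.** The nighttime PGIS is also rated at the randomization visit and one day before Weeks 26 and 54, about the same nights. Let a share s of the daily variance be common to same-night ADSD and PGIS, with the Step 3 assumption and φ = 0. The ADSD–PGIS change correlation is proportional to (1 + 1.143s)/√2.143 with one morning and (1 + 0.343s)/√1.343 with five. The ratio of the first to the second is 0.79 at s = 0, 1.06 at s = 0.5 and 1.26 at s = 1. Break-even is at s ≈ 0.37.

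**The case against.** The strongest reply is that no one-morning baseline has been specified for this endpoint. The second paragraph of SAP 4.2 ties its baseline to demographic summaries and to change analyses of efficacy, safety and PD endpoints. The nighttime ADSD is none of these. Protocol 6.9 places it in separate analyses, and SAP 2.1 lists no psychometric endpoint. The 7-day follow-up mean is likewise not written for nighttime. This stands in part: the mismatch is a literal reading of SAP 4.2 joined to an inference about follow-up. But SAP 4.2 says all assessments, Protocol Section 6 sends the definition of baseline to the SAP, and neither document offers another rule.

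Three stronger readings are tempting, and the documents do not support them.

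- A reader might infer that the schedule allows only one baseline morning. It provides five; the limit comes from the SAP rule.
- A reader might infer that baseline noise dominates the change score. Only the share of day-to-day noise follows from the schedule, given a 7-day mean and an assumed φ. The share of total variance could be 7% or 78% (Step 2).
- A reader might infer that the instrument must look less responsive than it is. For the PGIS the one-morning baseline can raise the correlation, because both ratings describe the same night (Step 4).

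One could also object that averaging brings in mornings before the run-in placebo dose. That is true, but the daytime baseline is taken entirely from before Week 0.

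**Conclusion.** The point holds as a minor specification weakness. On the literal SAP rule, one of five collected mornings serves as the nighttime baseline. With a 7-day follow-up mean it supplies about 70% to 88% of the day-to-day noise in the change. Averaging all five lowers that noise from 1.14 to 0.34 daily variances with independent days, and by roughly half to two-thirds under the positive correlations tried. Better reliability of the change follows if patients' true levels are stable across the pre-treatment mornings. A stronger PGIC correlation also requires the PGIC to be unrelated to baseline-morning noise. No direction can be claimed for the PGIS.

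The figures rest on the inferred 7-day mean and on assumed correlations, since the documents give none. The consequence is confined to the exploratory psychometric analysis in Protocol 6.9. The nighttime ADSD does not appear in the testing hierarchy of SAP Table 1, and no primary or secondary endpoint uses it.

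**What to change.** Amend the SAP only:

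1. Add the nighttime ADSD to the exceptions in SAP 4.2. Define its baseline as the mean of the available pre-randomization nighttime scores, with a stated minimum number of days.
2. Apply the daytime weekly-average and missing-day rule to the seven mornings before Weeks 26 and 54, and state which items enter the nighttime score. The daytime score uses six of the seven.
3. Because the PGIS shares the randomization morning, also report the PGIS correlation with the last-value baseline as a check.

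The cost is a few sentences and no new data. Adding pre-randomization mornings to the diary is no longer possible, because SAP 2.2 reports 502 patients already randomized. SAP Section 1 bars changes at or after the 54-week analysis, so the rule should be fixed before then. That also avoids a choice among several possible baselines after the data are seen.
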